### Feedback

---

Close Comment

Closed.

## Protocol Close Request Form

**Protocol Type****Are you requesting to close a IRB, sIRB, or hSCRO protocol?**

## IRB (UCI is the IRB of Record)

### IRB Closing Instructions

- An IRB protocol may be closed once subject accrual has ended, research interventions and data collection are complete, and analyses of subject identifiable data have concluded.
- The official retention period for UCI's IRB records begins on the date a closing report is submitted by the Lead Researcher (LR).

For more information, visit:

- [Protocol Closure](#)
- [Lead Researcher's IRB Recordkeeping Responsibilities](#)

### Closure Status

#### **Closing criteria:**

- All subject specimens, records, data have been obtained (i.e., no further collection is required).
- No further contact with subjects is necessary (i.e., all interactions or interventions are complete).
- Analysis of subject identifiable data, records, and specimens are complete (i.e., use or access to subject identifiable data and review of source documents by study sponsors is no longer necessary).

### **Please mark the option that represents the closing status of subject enrollments:**

Subject enrollment and research procedures are complete. This study meets the above criteria and can be closed.

### **Have there been any problems that required prompt reporting**

**to the UCI IRB?**

Yes, the problem(s) was previously reported to the IRB

**Have there been any complaints from UCI participants or others that required reporting to the UCI IRB?**

No

**Provide a brief summary of the project's results (preliminary or final):**

Due to low enrollment, the study was closed after enrolling 8 participants out of the planned 105. Although data collection is complete, data analysis has not yet been conducted. We plan to complete the analysis and submit the results to ClinicalTrials.gov by the reporting deadline of December 10, 2026.

**Closure Attachments (Optional)****Submit any supporting documents for the closure in the Attachments section below.**

---

**End of form. Please review responses for accuracy and**

and of the review response for accuracy and completeness.

### Project Screener

Submit a Human Subject Protocol for UCI Institutional Review Board (IRB) Review

Will this protocol be reviewed under a sIRB process?

No, there is no reliance involved. UCI serves as the IRB of record

Are the research procedures limited to the use/analysis of identifiable private information and/or identifiable biospecimens (no subject contact)?

No

Select the required **level of review** for this protocol:

Greater than Minimal Risk (Full Committee)

Check all sites where UCI investigator(s) will conduct research activities (e.g., recruitment,

informed consent, and research procedures including accessing identifiable, private information about participants):

UCI Facilities or Sites (e.g. school, hospital or clinics, etc.)

---

Provide a non-technical summary of the project that can be understood by IRB/hSCRO members with varied research backgrounds, including non-scientists and community members (**this summary should not exceed more than 250 words**):

Opioids are known to produce excellent intraoperative and postoperative pain relief. However, their effects can be limited by unwanted side effects such as nausea, constipation, itchiness, sedation, and respiratory depression. Additionally, their use perioperatively has been shown to result in the development of tolerance and hyperalgesia. Opioid-induced hyperalgesia (OIH) is a paradoxical increase in pain sensitivity following opioid exposure. OIH has been noted with many different opioids, but the most clinically well-documented hyperalgesic effect is with remifentanyl. Studies have attempted to reduce the development of tolerance and hyperalgesia through various agents. Their role in pain management is thought to decrease reported pain, increase the time to the patient's first request for pain medication, and lower the cumulative dose of pain medications over the first 48 hours postoperatively. Recent research by [name] have shown the mechanism for OIH in rats is due to an alteration in opioid receptor signaling and activation and hypertrophy of spinal glial cells (gliosis), and that this response can be attenuated by ultra-low dose opioid antagonists. However, there are no prospective, randomized clinical studies that have evaluated the effects ultra-low dose opioid antagonist naloxone on preventing OIH. The purpose of this study is to evaluate whether using ultra-low dose naloxone, an opioid antagonist, has the potential to block remifentanyl-induced hyperalgesia and tolerance following surgery. There are 3 study groups: (1) low dose remifentanyl infusion (LO, titrated from 0 to 0.2 mcg for an estimated average of 0.1 micrograms/kg/min), (2) high dose remifentanyl infusion combined with placebo (HI, titrated from 0.3 to 0.5 mcg for an estimated average of 0.4 micrograms/kg/min), or (3) high dose remifentanyl infusion combined with

ultra-low dose naloxone (HN, titrated from 0.3 to 0.5 mcg for an average of 0.4 micrograms/kg/min remifentanil with 0.004 micrograms/kg/min naloxone). The hypothesis of the study is that occurrence of remifentanil-induced hyperalgesia (low score in mechanical pain threshold) in the HN group will be lower than in the HI group. Adult patients (over 18 years old) undergoing similar surgeries will be selected via routine clinical care. Patients who consent to participate in the study will be administered naloxone or placebo alongside Remifentanil and data will be collected using self-reported and physiological measures.

## Instructions

### IRB Protocol Instructions

- For research with a Master Protocol or with a detailed project proposal, specify this in the protocol and an abbreviated protocol will be generated.
- Submit all new and/or revised supporting documents in the Protocol Attachments section near the end of the protocol.
- The Lead Researcher (LR) is responsible for maintaining all supplemental documentation (as indicated in the form) in the research records. This documentation may be requested by Human Research Protections for quality assurance review.

For regulatory or institutional guidance:

- Visit [Human Research Protections](#)
- Contact the [Human Research Protections staff](#)

For technical issues or questions:

- Visit the [Kuali Research Protocols \(KRP\) User Guide](#)
- Contact [Electronic Research Administration \(ERA\)](#)

## Type of Research

The purpose, specific aims or objectives of the research is:  
Biomedical

The research protocol is:  
Investigator-Initiated

Does the investigator-initiated study have any industry support?  
No

Does this study include a Master Protocol or detailed project proposal?  
No

Is this study an extension of a UCI IRB approved study (e.g., resubmission of ongoing exempt research; Open Label Extension) or is it otherwise related to a UCI IRB approved study?  
No

Does this research meet the definition of a [clinical trial](#) that requires adherence to [Clinicaltrials.gov](#)?  
Yes

If currently available, provide the [CT.gov](#) registration NCT # (Enter 8-digit sequence of numbers only):  
03066739

Specify the rationale for [Clinicaltrials.gov](#) registration:  
Applicable Clinical Trial

**STOP!** All clinical trials must be conducted under the auspices of an Organized Lead Unit (OLU). Please update. Go to Project Details and choose the appropriate OLU for the trial.

## Study Funding

Select the funding source(s) (**check all that apply**):

Department or campus funds (includes department support, unrestricted funds, start-up funds, personal funds, campus program awards, etc.)

### Scientific/Scholarly Review

Is the research Sponsor-Initiated?

No

Is the research cancer-related?

No

**The proposed research qualifies as greater than minimal risk, investigator-initiated biomedical research.** For greater than minimal risk biomedical research that is investigator initiated and has not been peer reviewed, Biostatistics, Epidemiology and Research design (BERD) review is required. The UCI IRB will review the research for scientific merit in conjunction with the expertise of the BERD) unit of the Institute for Clinical and Translational Science (ICTS). The UCI IRB staff will coordinate the review process.

Please click on the following link to arrange a consultation with one of the ICTS BERD Statisticians: [ICTS BERD Statisticians - Consultations](#)

Greater than Minimal Risk Non-Cancer, Investigator Initiated Biomedical Research - IRB / BERD Review Required

### Data Safety Monitoring Plan

Does this protocol require a DSM plan?

Yes

Provide details of those individuals who will be responsible for the safety oversight of your protocol, including the relevant experience/expertise of each individual (for UCI investigator initiated studies conducted only at UCI, provide the names and titles as well):

The board will be comprised of the Department of Anesthesiology and Perioperative Care Research Council. The council is composed of

researchers, educators, and administration that oversee all aspects of research of the department. One of the duties of the council is to ensure the safety of all research being conducted with the department. The Members are the following: [name], Chair of the Department of Anesthesiology & Perioperative Care; [name], Associate Clinical Professor and Director of the Medical Education Simulation Center; [name], Associate Clinical Professor; and [name], Assistant Professor and Director of the [name] Research Lab.

Indicate how frequently accumulated protocol data will be reviewed and evaluated for participant safety, protocol conduct and progress, and, when appropriate, efficacy:

The committee meets in-person or via Zoom on a quarterly basis. They also communicate on a regular basis with research updates.

Describe the events that would trigger an unscheduled review. Also include stopping guidelines and un-blinding rules if applicable:

Events such as protocol deviations, adverse events and major changes to the approved study protocol would trigger an unscheduled review.

List who will be *locally* monitoring and collecting information on adverse events and/or unanticipated problems (e.g., UCI Lead Researcher, Research Coordinator, etc.). Include the name, title and experience of the individual(s) and further describe each individual's role in the oversight of subject/patient participating in the protocol:

Aside from the lead researcher, [name], who is a senior CRC and the Clinical Research Supervisor, will be locally monitoring and collecting information on adverse events and/or unanticipated problems.

Describe the plan for annual reporting of the participants' safety, and the protocol's conduct, progress, and efficacy, when appropriate:

The PI will submit a CPA to the IRB for annual reporting of study progress, participants' safety and enrollment status.

## Potentially Hazardous Materials

If any of the following hazardous materials are involved in this research please check below:  
N/A

## Other UCI Committee Reviews

Check all ancillary committees that apply:  
N/A

## Supplemental Documents

Does this study include supplemental documents?

No

## Background & Purpose of the Research

Describe the purpose, specific aims or objectives and specify the hypotheses or research questions to be studied:

Opioid antagonists at ultra-low doses have been used with opioid agonists to prevent or limit opioid tolerance. Remifentanyl, a rapid onset/offset opioid that is often used as an anesthesia adjunct intraoperatively, has been associated with the development of hyperalgesia and opioid tolerance postoperatively. [1-4] Opioid-induced hyperalgesia (OIH) induced by remifentanyl intraoperatively may be a factor contributing to an increase in postoperative pain as well as difficulty in controlling such pain. The

purpose of this study will be to evaluate whether an ultra-low dose of naloxone, an opioid antagonist, could block remifentanil-induced hyperalgesia and tolerance following surgery.

Provide the scientific or scholarly rationale for the research and describe the relevant background information and the specific gaps in current knowledge that this study intends to address:

This research will help elucidate the degree of OIH after surgeries involving remifentanil and determine if a new technique can be employed to decrease remifentanil-induced OIH. By mitigating OIH, patients should have a decrease in postoperative pain and an increase in patient satisfaction at UCI and other hospitals where such a technique is employed.

Provide relevant preliminary data (animal and/or human):

Attempts have been made with various agents to reduce the development of tolerance and hyperalgesia following remifentanil. Postoperative hyperalgesia and its prevention has been studied with ketamine[10, 11, 15-36], Magnesium [12, 34, 37], Gabapentin[16], Clonidine[19, 38], Lornoxicam [18], Dextromethorphan [39], Paracetamol [40, 41], Morphine [42], Dexmedetomidine [43], Adenosine [44, 45], COX inhibitors [46, 47], Amantadine [48], Nitrous oxide [49], Fentanyl [50], Pregabalin [51], Buprenorphine [52], Midazolam [53], Dexamethasone [36]. Relevant to our current hypothesis is the report that concomitant administration of ultra-low dose naloxone [13] and naltrexone [54] with remifentanil prevented OIH. However, there are no studies on reducing the adverse effects of remifentanil with ultra-low dose naloxone in human subjects. While the traditional role of opiate antagonists have been in cases of opioid overmedication, recent evidence is emerging regarding their use in pain management. Gan et al. 1997 used an ultra-low dose naloxone infusion (0.00025 mg/kg/h or 0.001 mg/kg/h) in postoperative patients receiving IV morphine via a patient-controlled analgesia (PCA) device. Good pain relief was experienced in all groups, however consumption of PCA morphine was significantly reduced in patients that received the lowest infusion of naloxone and opioid-induced side effects (nausea, vomiting, pruritus) were reduced by naloxone at both dose.

Describe the primary outcome variable(s), secondary outcome variables, and predictors and/or comparison groups as appropriate for the stated study objectives/specific aims:

The primary outcome variable of the study will be to determine the occurrence of OIH in high dose remifentanyl treatment group compared to a low dose Remifentanyl group and a high dose Remifentanyl dose with ultralow dose naloxone. OIH will be determined by assessing evoked pain thresholds. Secondary outcomes will include verbal assessment of overall pain levels via validated standard pain questionnaires and post-operative opioid consumption to determine presence of opioid analgesic tolerance. The predicted outcome is that ultralow dose naloxone will attenuate the development of remifentanyl-induced OIH. Primary outcome: Mechanical pain threshold, determined by von Frey filaments, around the incision site at 24 and 48h post-surgery. Primary hypothesis: The mechanical pain thresholds at 48h in the HN group is higher than in the HI group. Secondary

hypotheses: 1. The mechanical pain thresholds at 48h in the LO group is higher than in the HI group. 2. The mechanical pain thresholds at 24h in both HN and LO group is higher than in the HI group. Secondary outcomes: - Opioid consumption required to control pain over the first 24 and 48h post-operatively. - Cold pressure test for pain threshold and pain tolerance - VAS pain scores measured prior to surgery and at 4, 8 and 12h after extubation and again at 24h and 48h post-operatively. - McGill short form questionnaire to be filled out prior to surgery and at 48h post-operatively - Brief Pain Inventory questionnaire to be filled out prior to surgery and at 48h post-operatively Other data collected will include a baseline history questionnaire (for demographics, age, sex, weight, income level) and the Public Health Questionnaire (PHQ-9) to measure depression as mood greatly influences pain perception. The PHQ-9 will be used to determine whether groups have been stratified appropriately.

List up to ten relevant references/articles to support the rationale for the research:

1. Bekhit, M.H., Opioid-induced hyperalgesia and tolerance. *Am J Ther*, 2010. 17(5): p. 498- 510. 2. Lin, S.L., et al., Co-administration of ultra-low dose naloxone attenuates morphine tolerance in rats via attenuation of

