kept in the research folder, which is kept in the hospital or shredded when it is not needed. If subject data is kept on a computer, the data will only be stored on hospital computers. Subject information will not be shared beyond the IRB approved research team as listed in Section 2 of this protocol narrative. Once consented, the subjects will be randomized by the study team into one of the three study groups: (1) low dose remifentanyl, (2) high dose remifentanyl combined with ultra-low dose naloxone or (3) high dose remifentanyl combined with placebo. The randomization list will be prepared before the study starts using a random number table generator and the study coordinator will obtain the information for each subject after consent. Personnel directly involved in subject care will be blinded as to naloxone or placebo administration. The pain assessors (second blinded group) will be blinded. Surgical procedures will not be altered and subjects will still receive standard subject care. Following consent, a packet of questionnaires (includes baseline questionnaire, Public Health Questionnaire (PHQ-9), VAS, McGill Short Form, Brief Pain Inventory) will be provided to subjects by study staff. All subjects will be required to complete a baseline questionnaire to obtain subject demographics prior to surgery. Opioid-induced hyperalgesia OIH will be measured by determining experimentally induced pain thresholds and clinically meaningful outcomes of pain via validated pain questionnaires and post-operative opioid consumption. These outcomes have previously been used and validated to assess remifentanyl-induced hyperalgesia; pain thresholds to cold and static mechanical stimulation are the most common pain modalities altered by remifentanyl infusion. Experimentally induced pain will be performed in pre-op by quantitative sensory testing via von Frey filaments applied in ascending order to the dorsal surface of the subject's non-dominant hand and 5cm from the incision site. Subjects will be instructed to indicate when stimulus produces a painful sensation as well as when the stimulus becomes unpleasant. In addition to determination of mechanical pain thresholds, cold pain threshold and tolerance will be determined. Subjects will be instructed to immerse their hand in a bucket of ice water and indicate when they first experience a painful sensation (threshold) and to remove their hand from the ice water when they can no

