 Subjects screened for inclusion/exclusion criteria Study introduction  
 during surgical consult visit Subjects provided with consent form and study  
 information sheet 2 Lab Visit Initiate subject consent Hamilton Rating  
 Scale, VAS, McGill Pain Questionnaire, Brief Pain Inventory Finalize Consent  
 3 Pre-Surgery Subject is greeted in preop area Von Frey Testing, Cold  
 Pressor Test, Opioid Consumption Pre-surgery medication: standard-of-  
 care 4 Surgery Group 1 (LO): Induction dose per anesthesiologist (no  
 ketamine); Maintenance: 0.1mcg Remifentanyl Group 2 (HI): Induction dose  
 per anesthesiologist (no ketamine); Maintenance: 0.4mg Remifentanyl +  
 Saline Group 3 (HN): Induction dose per anesthesiologist (no ketamine);  
 Maintenance: 0.4mg Remifentanyl + 0.004mcg/kg/min Naloxone 5 Post-  
 Surgery Post-surgery medication: standard-of-care @4H, @8H, @ 12H: VAS,  
 Opioid Consumption @24H: VAS, Von Frey Testing, Cold Pressor Test,  
 Opioid Consumption @48H: Hamilton, VAS, McGill, Brief Pain Inventory,  
 Von Frey, Cold Pressor, Opioid Consumption UCI IRB

Provide precise definitions of the study endpoints and criteria for evaluation; if the primary outcomes are derived from several measurements (i.e., composite variables) or if endpoints are based composite variables, then describe precisely how the composite variables are derived:

see above

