### **Statistical Considerations**

Is a statistical analysis plan appropriate for this qualitative study design?

Yes

Describe the statistical methods for the stated specific aims and hypotheses. Your analysis plans should match the stated study specific aims and hypotheses:

For the primary outcome, the 2-sample t-test will be applied to compare the difference in mechanical pain thresholds at 24 and 48h between HN and HI group, and between LO and HI group. For the secondary outcomes, the continuous variables will also be analyzed using 2-sample t-test to identify the difference between HN and HI group, and between LO and HI group. The mean level and corresponding 95% confidence interval (CI) will be

obtained for each study group. The categorical outcomes will be analyzed using the chi-square test and the odds ratio (compare to HI group) and corresponding 95% CI will also be obtained.

Describe the statistical method(s) that will be used to analyze the primary outcome(s) or endpoints:

see above

If appropriate describe secondary or post hoc analyses of primary outcome(s) or other exploratory analysis and if necessary, provide a breakdown of the methods used per outcome or endpoint:

Secondary outcomes: - Opioid consumption required to control pain over the first 24 and 48h post-operatively. - Cold pressure test for pain threshold and pain tolerance - VAS pain scores measured prior to surgery and at 4, 8 and 12h after extubation and again at 24h and 48h post-operatively. - McGill short form questionnaire to be filled out prior to surgery and at 48h post-operatively - Brief Pain Inventory questionnaire to be filled out prior to surgery and at 48h post-operatively

**Sample Size Determination:** Explain how the overall target sample size was determined (e.g., power analysis; precision estimation), providing justification of the effect size for the primary outcome based on preliminary data, current knowledge/literature and/or cost consideration; if appropriate, provide sample size justification for secondary outcomes. Power analysis should (at least) match the primary outcome/endpoint:

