### **Research Procedures**

Provide a detailed chronological description of the clinical or treatment plan:

see above

Specify the total duration of a subject's participation in the study and clearly outline the duration of participation for each study visit and sub-study, as applicable:

see above

List data collection tools (e.g., measures, questionnaires, observational tool) below by clicking the 'Add Line' button. Include additional rows for study instruments, as needed:

The 'Columns' button allows you to display or hide columns in the Study Instrument List.

Name of Tool:

Cold Pressor Test

Is the data collection tool standardized or validated?

Yes

Please provide data collection tool citation:

[https://www.jpain.org/article/S1526-5900\(04\)00746-1/fulltext](https://www.jpain.org/article/S1526-5900(04)00746-1/fulltext)

Name of Tool:

PHQ 9

Is the data collection tool standardized or validated?

Yes

Please provide data collection tool citation:

<https://www.apa.org/pi/about/publications/caregivers/practice-settings/assessment/tools/patient-health>

Name of Tool:

Pain Scores (VAS, SF McGill, Brief Pain Inventory)

Is the data collection tool standardized or validated?

Is the data collection tool standardized or validated?

Yes

Please provide data collection tool citation:

<https://pubmed.ncbi.nlm.nih.gov/22588748/>

Name of Tool:

Von Frey

Is the data collection tool standardized or validated?

Yes

Please provide data collection tool citation:

<https://www.sciencedirect.com/topics/medicine-and-dentistry/von-frey-hair>

Name of Tool:

Hamilton Rating Scale

Is the data collection tool standardized or validated?

Yes

Please provide data collection tool citation:

<https://academic.oup.com/occmed/article/65/7/601/1733495>

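### The protocol calls mood influential but uses the PHQ-9 only to check a stratification it does not describe; a pre-specified baseline adjustment would use the data better, and the mood instrument needs reconciling.

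*Combined protocol and SAP*

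**What the plan says.** **Role of the PHQ-9.** The Background & Purpose of the Research section lists the PHQ-9 among other data, collected "to measure depression as mood greatly influences pain perception". It then states the score's only use: "The PHQ-9 will be used to determine whether groups have been stratified appropriately".

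**Allocation.** The Study Design form field asks for any stratification scheme. The answer gives three groups and says: "The randomization list will be prepared before the study starts using a random number table generator". It names no strata, blocks or minimisation.

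**Analysis.** Under Statistical Considerations, "the 2-sample t-test will be applied to compare the difference in mechanical pain thresholds at 24 and 48h between HN and HI group", and likewise between LO and HI. Secondary continuous outcomes also get two-sample t-tests, and categorical ones chi-square tests. No baseline variable enters any model.

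**Mood instrument.**
- The packet handed out after consent (Study Design) "includes baseline questionnaire, Public Health Questionnaire (PHQ-9), VAS, McGill Short Form, Brief Pain Inventory". It does not mention a Hamilton scale.
- The stepwise visit schedule at the end of Study Design reads "2 Lab Visit Initiate subject consent Hamilton Rating" for the baseline visit and "48H: Hamilton, VAS, McGill, Brief Pain Inventory" for the last assessment. It does not mention the PHQ-9.
- The timing table in Study Design names the PHQ-9, but its layout is broken in the available text and the time points cannot be read.
- The instrument list under Research Procedures has the PHQ-9 and, as a separate entry, the "Hamilton Rating Scale".
- A PHQ-9 survey is among the attachments.

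**The concern.** There are two separate points.

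The first concerns use of the data. The protocol names a factor it regards as influential and measures it before surgery. It then uses it only to judge after the fact whether the groups came out as intended. No criterion is given for that judgement and no action follows from it. Looking at balance does not change the treatment estimate; a covariate fixed in advance does. The same holds for the von Frey threshold, which is measured pre-operatively near the incision site but is not in the primary analysis. At stake is some power, and some protection against an estimate that chance differences between the groups have moved.

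The second concerns consistency. A reader cannot tell from the documents whether each patient should have a PHQ-9, a Hamilton scale or both, or when. A site that worked only from the stepwise schedule would have no PHQ-9 with which to make the stated comparison.

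**Working it through.** **1. The plan's own figures.** Inputs from Sample Size Determination: two-sided t-test, alpha 0.05, 105 recruited (35 per group), 96 analysed, hence 96/3 = 32 per group. The noncentral t distribution gives a detectable effect of 0.7115 SD at 80% power and 0.8232 SD at 90%. The stated 0.71 and 0.82 reproduce, and 96 is consistent with 105 less 8% (105 × 0.92 = 96.6). This point does not disturb the sample size.

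**2. How large can chance imbalance be?** With unstratified allocation and 32 per group, the difference between two group means of a standardised baseline score has SD √(2/32) = 0.25. The 95% chance range is ±1.96 × 0.25 = ±0.49 SD.

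**3. What would that do to the unadjusted HN–HI estimate?** The shift is r × imbalance, where r is the correlation of the PHQ-9 with the 48-hour threshold. The documents give no r, so a range is assumed.

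| Assumed r | Shift at a typical imbalance (0.25 SD) | Shift at the edge of the 95% range (0.49 SD) | Edge shift as share of 0.71 |
|---|---|---|---|
| 0.2 | 0.050 | 0.098 | 14% |
| 0.3 | 0.075 | 0.147 | 21% |
| 0.4 | 0.100 | 0.196 | 28% |

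The standard error of the unadjusted contrast is itself 0.25 SD and already includes this source of variation. Every shift in the table lies inside one standard error.

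**4. What would adjustment for the PHQ-9 alone gain?** Residual variance is multiplied by 1 − r², so the standardised effect becomes 0.7115/√(1 − r²). With 32 per group and one further degree of freedom spent:

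| Assumed r | Variance removed | Effective effect | Power |
|---|---|---|---|
| none | 0% | 0.712 | 80.0% |
| 0.2 | 4% | 0.726 | 81.6% |
| 0.3 | 9% | 0.746 | 83.6% |
| 0.4 | 16% | 0.776 | 86.3% |

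**5. What would the PHQ-9 add beside baseline threshold?** As an illustration, with every value assumed: baseline and 48-hour threshold correlate 0.5, and the PHQ-9 correlates 0.3 with each. The partial correlation of the PHQ-9 is (0.3 − 0.5 × 0.3)/√[(1 − 0.25)(1 − 0.09)] = 0.15/0.826 = 0.18. Its square is 0.033, so the PHQ-9 removes about 3% of the remaining variance, not 9%. Power is about 89.9% with baseline threshold alone and 90.8% with both. Under these assumptions most of the gain comes from the baseline threshold.

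**6. The instruments side by side.** The PHQ-9 appears in Background & Purpose, the post-consent packet, the timing table, the instrument list and the attachments. The Hamilton scale appears in the stepwise schedule and the instrument list. The two sets overlap only in the instrument list, where they are separate tools.

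**The case against.** The case on the other side has five parts.

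- **The unadjusted t-test is valid.** This stands. Under randomisation it is unbiased, and its standard error covers chance imbalance in every covariate. A reader might infer from the table in step 3 that the planned comparison is biased by mood. The documents do not support that: the shifts describe one unlucky allocation, not a systematic error.
- **Stratified may loosely mean balanced.** This is plausible, and the sentence would then promise an ordinary baseline comparison. Even so, the plan says neither what counts as acceptable nor what follows if the groups differ.
- **The PHQ-9 has not been dropped.** This stands. A reader of the stepwise schedule alone might infer that the Hamilton scale replaced it, but several other places name the PHQ-9. Nor do the documents say which Hamilton scale is meant. What they show is an inconsistency. It is also not the reason mood is missing from the analysis, which is simply that the planned tests are unadjusted.
- **The gain is assumed.** This stands. No correlation between the PHQ-9 and von Frey threshold is given. The exclusion of psychiatric illness may narrow the range of scores and weaken any correlation, and step 5 shows how little may remain once baseline threshold is in the model.
- **Only 8 patients were enrolled.** This stands for the analysis still to be done. The closure form reports 8 of a planned 105, at which size covariate adjustment is not realistic.

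**Conclusion.** The point holds as a modest improvement to the analysis plus a documentary inconsistency. The plan names mood as influential and measures it at baseline, but uses it only to check a stratification that is nowhere described, with no rule for acting on the result. Pre-specified adjustment would make better use of data already collected.

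At the planned 32 per arm the gain from the PHQ-9 alone is about 2 to 6 percentage points of power for an assumed r of 0.2 to 0.4, and probably less beside baseline threshold. The sample size calculation is unaffected, and the primary test as planned remains valid. For the 8 patients enrolled, the practical consequences are to make clear which mood instrument was given and to report it descriptively.

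**What to change.** 1. In Background & Purpose, replace the sentence on stratification with a statement that baseline PHQ-9 will be summarised by group and used as a covariate.
2. In Statistical Considerations, pre-specify an ANCOVA of the 48-hour mechanical threshold, HN versus HI, adjusting for baseline von Frey threshold (the site near the incision) and baseline PHQ-9.
3. Reconcile the packet description, timing table, stepwise schedule and instrument list on one mood instrument and its time points. The PHQ-9 is the natural candidate, being already in the baseline packet. If a Hamilton scale is also kept, say which one and for what purpose.
4. For the 8 patients enrolled, list or summarise baseline PHQ-9 by group without adjustment, and state which mood instrument was actually given. The closure form says the analysis has not yet been conducted, so this can be settled before results are reported.

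The cost is plan wording, a corrected visit list, and about one degree of freedom per covariate (two of the 62 available in a 32-per-arm comparison). No new data collection is needed if the packet was used as described.
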